4.7.3 Adverse events

General common rules for adverse events (AEs)

All AEs will be coded to a lower-level term (LLT), preferred term (PT), high-level term (HLT), high-level group term (HLGT), and associated primary system organ class (SOC) using the Medical Dictionary for Regulatory Activities (MedDRA) currently in use by the sponsor at the time of database lock.

The AEs will be analyzed in the following 3 categories (as defined by study periods for the safety analyses):

- Pre-treatment AEs: AEs that developed, worsened or became serious during the pre-treatment period.
- Treatment-emergent adverse events (TEAEs): AEs that developed, worsened or became serious during the on-treatment period
- Post-treatment AEs: AEs that developed or worsened, or became serious during the post-treatment period

Similarly, deaths will be analyzed in the pre-treatment, treatment-emergent and post-treatment periods.

The primary focus of AE reporting will be on TEAEs. Pre-treatment and post-treatment AEs will be described separately.

An AE with incomplete or missing date/time of onset (occurrence, worsening, or becoming serious) will be classified as a TEAE unless there is definitive information to determine it is a pre-treatment or a post-treatment AE.

If the assessment of the relationship to IMP is missing for an AE, this AE will be assumed as related to IMP. If the severity is missing for 1 of the treatment-emergent occurrences of an AE, the severity will be imputed with the maximal severity of the other occurrences. If the severity is missing for all the occurrences, the severity will be left as missing.

Multiple occurrences of the same event in the same participant will be counted only once in the tables within a treatment phase.

The AE tables will be sorted as indicated in [Table 5](#).

Table 5 - Sorting of AE tables

AE presentation	Sorting rules
SOC, HLGt, HLT and PT	By the internationally agreed SOC order and by alphabetic order of HLGts, HLTs and PTs.
SOC and PT	By the internationally agreed SOC order and decreasing frequency of Pts ^{a,b}

a Sorting will be based on the Gla-300 group/overall incidence. In case of equal frequencies of PTs within a SOC, the alphabetic order will be applied.
b The table of all TEAEs presented by SOC and PT will define the presentation order for all other tables (eg, treatment-emergent SAE) presented by SOC and PT, unless otherwise specified.

Analysis of all adverse events

The overview of all TEAEs with the details below will be generated:

- Any TEAE
- Any severe TEAE
- Any treatment emergent serious adverse event (SAE)
- Any TEAE leading to death (death as an outcome of the AE as reported by the Investigator in the AE page)
- Any TEAE leading to study discontinuation
- Any TEAE leading to permanent discontinuation of IMP
- Any treatment emergent AESI
 - Pregnancy
 - Symptomatic overdose
 - Alanine aminotransferase (ALT) increase
- Any TEAE related to local intolerance at the injection site or hypersensitivity reaction
- Any treatment-related TEAE

The AE summaries of [Table 6](#) will be generated with number (%) of participants experiencing at least one event. A bar chart will also be produced for the percentage (%) of participants experiencing common TEAEs ($\geq 5\%$) in any treatment group, presented both overall and by SOC and PT.

Table 6 - Analyses of adverse events

Type of AE	MedDRA levels
All TEAE	Primary SOC, HGLT, HLT and PT
Common TEAE ($\geq 5\%$)	Primary SOC, HGLT, HLT and PT
TEAE related to IMP as per Investigator's judgment	Primary SOC and PT
TEAE by maximal severity	Primary SOC and PT
Treatment emergent SAE	Primary SOC and PT
TEAE leading to permanent discontinuation of IMP	Primary SOC and PT
TEAE leading to study discontinuation	Primary SOC and PT
Treatment emergent AESI	Primary SOC and PT
TEAE related to local intolerance at the injection site or hypersensitivity reaction	Primary SOC and PT
TEAE leading to death (death as an outcome of the AE as reported by the Investigator in the AE page)	Primary SOC and PT
Pretreatment AE	Overview ^a
	Primary SOC and PT
Post-treatment AE	Overview ^a
	Primary SOC and PT
Post-treatment SAE	Overview ^a
	Primary SOC and PT

^a Will include the following AE categories: any AEs, any severe AEs, any SAEs, any AEs leading to death, any AEs leading to study discontinuation, any AEs leading to permanent discontinuation of IMP, any AESIs, and any treatment-related AEs.

Analysis of deaths

In addition to the analyses of deaths included in [Table 6](#) the number (%) of participants in the following categories will be provided:

- Deaths during the treatment-emergent and post-treatment periods and reasons for death
- Deaths in non-randomized participants or randomized but not treated participants

Analysis of adverse events of special interest (AESIs)

An AESI is an AE (serious or nonserious) of scientific and medical concern specific to the sponsor's product or program, for which ongoing monitoring and immediate notification by the investigator to the sponsor is required. Such events may require further investigation in order to characterize and understand them. Adverse events of special interest may be added, modified, or removed during the trial by protocol amendment. All AESIs will be reported to the Sponsor in the same timeframe as SAEs (within 24 hours).

The following AEs will be considered as AESIs in this trial:

- Pregnancy of a female participant enrolled in the trial, as well as pregnancy occurring in a female partner of a male participant enrolled in the trial with study drug/NIMP.

- Symptomatic overdose (serious or nonserious) with the study drug/NIMP.
- Increase in alanine aminotransferase (ALT; $>3 \times$ upper limit of normal [ULN])

Adverse events of special interest (AESIs) will be selected for analyses as indicated in [Table 7](#). Number (%) of participants experiencing at least one event will be provided for each event of interest. Tables will be sorted as indicated in [Table 5](#). A bar chart will also be used to present the percentage (%) of participants experiencing at least one treatment-emergent AESI, overall and by each event of interest.

Table 7 - Selections for AESIs

AESIs	Selection
Pregnancy	eCRF specific tick box on the AE page and Pregnancy All Items page
Symptomatic overdose	eCRF specific tick box on the AE page and Overdose page
ALT increase	eCRF specific tick box on the AE page

Analysis of local intolerance at the study drug injection site or hypersensitivity reactions

Any signs of local intolerance at the study drug injection site or hypersensitivity reactions should be recorded on the AE page of the eCRF. Number (%) of participants experiencing at least one event will be summarized, as well as at the primary SOC and PT level.

4.7.4 Additional safety assessments

4.7.4.1 Laboratory variables and vital signs

The following laboratory variables and vital signs variables will be analyzed from baseline to Week 24 per [Section 5.7](#). They will be converted into standard international units.

- Hematology:
 - Red blood cells and platelets: erythrocytes, platelet count, leukocytes, hemoglobin, hematocrit
- Clinical chemistry:
 - Metabolism: albumin
 - Electrolytes: sodium, potassium
 - Renal function: creatinine, eGFR, creatinine clearance. Creatinine clearance will be derived with the equation of Cockcroft and Gault using weight assessed at the same visit as creatinine. The central laboratory should calculate eGFR using the Chronic Kidney Disease Epidemiology Collaboration (CKD-EPI) equation:
$$\text{eGFR}_{\text{Cr}} = 142 \times \min(\text{Scr}/\kappa, 1)^\alpha \times \max(\text{Scr}/\kappa, 1)^{-1.200} \times 0.9938 \times \text{Age} \times 1.012$$
 [if female](6).
 - Liver function: ALT, aspartate aminotransferase (AST), alkaline phosphatase (ALP), total bilirubin, indirect bilirubin, direct bilirubin

- Urinalysis:
 - Quantitative analysis: pH, protein, ketones, leukocytes, blood/hemoglobin, glucose
- Pregnancy test: urine or serum
- Vital signs: body weight, heart rate, systolic blood pressure (SBP) and diastolic blood pressure (DBP) while in seated position

The tests detailed above will be performed at the central laboratory, except urine pregnancy tests, which will be performed at sites using urine pregnancy test kits that are provided by PPD. Additional tests may be performed at a local or central laboratory at any time during the trial, as deemed necessary by the investigator or required by local regulations. If a test is used to evaluate an AE (diagnostic, follow-up, outcome), the results (including the disease progression of CKD) must be entered into the CRF.

All laboratory tests with values that are considered clinically significantly abnormal during the trial should be repeated until the values return to normal/baseline or are no longer considered clinically significant by the investigator. Potentially clinically significant abnormalities (PCSA) will be flagged and the number and percentage of participants with PCSA will be presented.

Quantitative analyses

For all laboratory variables and vital signs above, descriptive statistics for results and changes from baseline will be provided for each analysis window, as well as the last value and the worst value (minimum and/or maximum value depending on the parameter) during the on-treatment period. These analyses will be performed using central measurements only (when available) for laboratory variables. A scatter plot of the worst post-baseline treatment-emergent value vs baseline value will also be presented by biological function and parameter.

Analyses according to PCSA

PCSA analyses will be performed based on the PCSA list in [Section 5.5](#). For parameters for which no PCSA criteria are defined, similar analyses will be done using the normal range, if applicable.

Analyses according to PCSA will be performed based on the worst value during the treatment-emergent period, using all measurements (either local or central, either scheduled, nonscheduled or repeated).

For laboratory variables and vital signs variables above, the incidence of participants with at least one PCSA during the treatment-emergent period will be summarized regardless of the baseline level and according to the following baseline status categories:

- Normal/missing
- Abnormal according to PCSA criterion or criteria

In addition to summary tables, the percentage (%) of participants with at least one abnormality (PCSA) during the treatment-emergent period will be presented using bar charts, by biological function and parameter.

4.7.4.2 *Product complaints*

All product complaint summaries during the on-treatment period (defined in [Section 4.1](#)) will be generated in the safety population and will include the number (%) of participants experiencing at least one event, the number of events and rate per participant-year.

The event rate per participant-year will be defined as the number of events divided by the cumulative duration of all participants' exposure expressed in years.

The overview of product complaints with the details below will be generated:

- Any product complaint
- Any product complaint related to AEs
- Any product complaint leading to incorrect IMP dose administration

In addition, the analyses below will be conducted.

- Any product complaint categorized by type of complaint
- AE(s) leading to product complaints by primary SOC and PT

4.8 OTHER ANALYSES

All analyses are appropriately described in other areas of the SAP.

4.9 INTERIM ANALYSES

No interim analyses are planned for this trial.

5 SUPPORTING DOCUMENTATION

5.1 APPENDIX 1 LIST OF ABBREVIATIONS

ADA:	American Diabetes Association
AE:	adverse event
AESIs:	adverse events of special interest
ALT:	alanine aminotransferase
ALP:	aspartate aminotransferase
ANCOVA:	analysis of covariance
AST:	aspartate aminotransferase
BMI:	body mass index
CGM:	continuous glucose monitoring
CKD:	chronic kidney disease
CKD-EPI:	Chronic Kidney Disease Epidemiology Collaboration
COVID-19:	coronavirus disease 2019
CV:	coefficient of variation
DBP:	diastolic blood pressure
DTP:	direct-to-patient
EASD:	European Association for the Study of Diabetes
eCRF:	electronic case report form
eDiary:	electronic diary
eGFR:	estimated glomerular filtration rate
EMA:	European Medicines Agency
FPG:	fasting plasma glucose
Gla-300:	insuline glargine 300 U/mL
GLP-1 RA:	glucagon-like peptide-1 receptor antagonist
GMI:	Glucose Management Indicator
HbA1c:	glycated hemoglobin
HCP:	healthcare provider
HLGT:	high-level group term
HLT:	high-level term
ICE:	intercurrent event
ICF:	informed consent form
IDeg-100:	insulin degludec 100 U/mL
IMP:	investigational medicinal product
ITT:	intent-to-treat
LLT:	lower-level term
LS:	least-squares
MAR:	missing at random
MCMC:	Markov chain Monte Carlo
MedDRA:	medical dictionary for regulatory activities
MI:	multiple imputation
MMRM:	mixed-effect model with repeated measures

MNAR:	missing not at random
NIMP:	non-investigational medicinal product
OAD:	oral antidiabetic drug
OR:	odds ratio
PCSA:	potentially clinically significant abnormality
PPS:	per protocol set
PT:	preferred term
SAE:	serious adverse event
SAP:	statistical analysis plan
SAS:	statistical analysis system
SBP:	systolic blood pressure
SD:	standard deviation
SE:	standard error
SGLT-2i:	sodium-glucose co-transporter-2 inhibitor
SMPG:	self-measured plasma glucose
SOC:	system organ class
SoE:	schedule of events
SU:	sulfonylureas
T2DM:	type 2 diabetes mellitus
TAR:	time above range
TBR:	time below range
TEAE:	treatment-emergent adverse event
TIR:	time in range
TITR:	time in tight range
ULN:	upper limit of normal
WOCBP:	woman of childbearing potential
WHO-DD:	World Health Organization-drug dictionary

5.2 APPENDIX 2 CHANGES TO PROTOCOL-PLANNED ANALYSES

Changes to protocol-planned analyses include the following:

- Multiplicity adjustments on secondary endpoints ([Section 4.1](#), [Section 4.4.1.2](#), [Section 4.6](#)).
- ~~CCI~~ compliance rules ([Section 4.5.1](#)).
- Analysis of exploratory endpoints - ~~CCI~~ ([Section 4.5.2](#)).

Due to study early termination, planned analyses have been reduced in accordance with an abbreviated CSR. The list of tables, listings and figures supporting the abbreviated CSR are documented in Appendix 6 ([Section 5.6](#)) and focus on demographics, disease characteristics at baseline, exposure, participant disposition and safety. Primary and secondary efficacy data is descriptively summarized.

5.3 APPENDIX 3 DEMOGRAPHICS AND BASELINE CHARACTERISTICS, MEDICAL (OR SURGICAL HISTORY), DISEASE CHARACTERISTICS AT BASELINE, PRIOR AND CONCOMITANT MEDICATIONS

The following demographics and baseline characteristics, medical and surgical history and disease characteristics at baseline, and prior and concomitant medications will be summarized for the ITT population. Continuous data will be summarized using descriptive statistics. Categorical data will be summarized using counts and percentages.

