8.7.6.3 Other Safety Analyses

The clinical safety laboratory test values, vital signs, and physical examination findings will be summarized by treatment arm. Potential clinically significant values will be flagged and summarized.

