1.2 OBJECTIVE AND ENDPOINTS

Table 2 - Objectives and endpoints

Objectives	Endpoints
Primary 
To demonstrate non-inferiority (with a margin of 0.3%) and, if achieved, to demonstrate the superiority in the efficacy of Gla-300 compared with IDeg-100 in terms of change in HbA1c from baseline to Week 24 in insulin-naïve participants with T2DM and renal impairment who have glycemic levels above target with OADs with or without GLP-1 RA	
HbA1c level: Change from baseline to Week 24
Secondary 
To evaluate the effects of treatment with Gla-300 compared with IDeg-100 on the clinical parametersTo assess the safety and tolerability of Gla-300 and IDeg-100	
FPG: Change from baseline to Week 24Fasting SMPG: Change from baseline to Week 247-point SMPG profiles: Change from baseline to Week 24, per time point within 24-hour periodPercentage (%) of participants reaching HbA1c target of <7.0% at Week 24Safety evaluations of the following (during the 24-week treatment period, during the titration period, and during the maintenance period):
All hypoglycemia eventsThe frequency of and diurnal distribution (all day, daytime (occurring between 06:00 and 23:59 inclusively), and nocturnal (occurring between 00:00 and 05:59 inclusively) of hypoglycemia by category (symptomatic, asymptomatic, severe) per the ADA/EASD hypoglycemia classificationLocal tolerability at injection siteHypersensitivity reactionsAdverse events (AEs) and serious adverse events (SAEs), including AESIs, and other safety evaluations, including vital signs and body weight

Objectives	Endpoints
Exploratory	 The content of this cell is completely redacted with a large black rectangular box.
	 The content of this cell is completely redacted with a large black rectangular box.

Objectives	Endpoints
CCI	

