5.6 APPENDIX 6 TABLE OF CONTENTS FOR ABBREVIATED CSR

	Title	Analysis Set
Table		
14.1.1.1	Participant Disposition	ITT Set
14.1.1.2	Analysis Sets	Screened Set
14.1.1.3	Number of Participants Screened	Screened Set
14.1.1.4	Number of Participants Screened by Country and Site	Screened Set
14.1.2	Significant Protocol Deviations	ITT Set
14.1.3.1	Demographics and Participant Characteristics at Baseline	Safety Set
14.1.3.2	Disease Characteristics at Baseline	Safety Set
14.1.4	Medical or Surgical History at Screening by Primary SOC and PT	ITT Set
14.1.5.1	Extent of Study Treatment Exposure	Safety Set
14.1.5.2	Treatment Compliance	Safety Set
14.1.5.3	Dosing Summary	Safety Set
14.2.1.1	Baseline Summary of Primary Endpoint: HbA1c Level	ITT Set

	Title	Analysis Set
14.2.1.2	Baseline Summary of Primary Endpoint: HbA1c Level by Subgroups	ITT Set
14.2.2.	Baseline Summary of Secondary Endpoints	ITT Set
14.3.1	Overview of Adverse Event profile: Treatment-emergent Adverse Events	Safety Set
14.3.2	Number (%) of Participants with TEAE(s) by Primary SOC, HLGT, HLT and PT	Safety Set
14.3.3.	Participants with a Common TEAE ($\geq 5\%$) in Any Treatment Group by Primary SOC, HLGT, HLT and PT	Safety Set
14.3.4	Number (%) of Participants with TEAE(s) Related to IMP as per Investigator's Judgment by Primary SOC and PT	Safety Set
14.3.5	Number (%) of Participants with Treatment-emergent SAEs by Primary SOC and PT	Safety Set
14.3.6	Number (%) of Participants Who Died by Study Period	Safety Set
14.3.7	Overview of Hypoglycemic Events Overall and by Observation Period, ADA Level, and Diurnal Distribution	Safety Set
Figure		
14.2.1.1	Box Plot of HbA1c Level by Analysis Visit (Observed Cases)	ITT Set
14.2.2.1	Box Plot of FPG Level by Analysis Visit (Observed Cases)	ITT Set
14.2.2.2	Box Plot of SMPG Level by Analysis Visit (Observed Cases)	ITT Set
14.2.2.3	Line Plot of 7-point SMPG Profiles, Per Time Point within 24-Hour Period by Analysis Visit (Observed Cases)	ITT Set
14.2.2.4	Bar Chart of Percentage (%) of Participants Reaching HbA1c $< 7.0\%$ at Week 24 (Observed Cases)	ITT Set
Listing		
16.2.1	Participant Randomization List	ITT Set
16.2.2	Listing of Participants with at Least One Protocol Deviation	ITT Set
16.2.3.1	Listing of Participant Demographics	Safety Set
16.2.3.2	Listing of Baseline Disease Characteristics	Safety Set
16.2.5.1	Exposure to IMP	Safety Set
16.2.7.1	Listing of all AEs	Safety Set
16.2.7.2	Listing of all AEs leading to study discontinuation	Safety Set

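### The abbreviated report keeps no post-baseline summary or listing of body weight, vital signs or safety laboratory values, and SAP Appendix 2 does not name them as dropped

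*SAP*

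**What the plan says.** - **Endpoints.** SAP 1.2, Table 2, lists under the safety objective "other safety evaluations, including vital signs and body weight". Laboratory values are not named in that row.
- **Planned analyses.** Protocol 8.7.6.3 states: "The clinical safety laboratory test values, vital signs, and physical examination findings will be summarized by treatment arm". SAP 4.7.4.1 opens its variable list with "The following laboratory variables and vital signs variables will be analyzed from baseline to Week 24". It then specifies the content: "For all laboratory variables and vital signs above, descriptive statistics for results and changes from baseline will be provided for each analysis window", together with the last and worst on-treatment values and PCSA incidence against the criteria in Table 12.
- **The reduction.** SAP 4.1 says that not all analyses were performed, because of early termination and lack of data. SAP 5.2 (Appendix 2) says that the remaining outputs "focus on demographics, disease characteristics at baseline, exposure, participant disposition and safety" and points to Appendix 6 for the list.
- **What Appendix 6 keeps for safety.** Tables 14.3.1 to 14.3.6 cover adverse events and deaths. Table 14.3.7 is the "Overview of Hypoglycemic Events Overall and by Observation Period, ADA Level, and Diurnal Distribution". Listings 16.2.7.1 to 16.2.7.4 cover adverse events, deaths and hypoglycemia.

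**The concern.** Two named safety endpoints, body weight and vital signs, have no post-baseline output in a report described as focusing on safety. The planned chemistry summaries are gone as well, in a population enrolled for eGFR from 15 to below 60, where creatinine and eGFR are measured for CKD monitoring.

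Adverse-event tables do not fully stand in for them. Under Protocol 6.2.5, abnormal laboratory findings tied to the underlying disease, and abnormal vital signs, are not reported as adverse events unless a further criterion is met. A weight change of 5%, which Table 12 treats as a PCSA, need not become an adverse event either.

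There is also a documentation gap. Protocol Section 8 says that changes from the planned analyses will be recorded in the SAP. A reader of Appendix 2 learns that outputs were reduced, but can discover that these analyses went only by comparing Appendix 6 with SAP 4.7.4.1.

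**Working it through.** No sample-size or error-rate figure bears on this point. The check is a match of outputs to definitions, plus date arithmetic.

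**1. Count of outputs in Appendix 6.** 21 tables + 5 figures + 10 listings = 36. No title mentions weight, vital signs, laboratory values, eGFR, ALT, creatinine or PCSA.

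**2. What the retained outputs contain by their SAP definitions.**

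| Parameter | Baseline | Post-baseline |
|---|---|---|
| Body weight | Table 14.1.3.1, "Demographics and Participant Characteristics at Baseline"; SAP 5.3.1 includes weight | none |
| Heart rate, SBP, DBP | none | none |
| eGFR | Table 14.1.3.2, "Disease Characteristics at Baseline"; SAP 5.3.3 includes eGFR | none |
| ALT | none | no values; ALT increase above 3 x ULN appears as an event of special interest in Table 14.3.1 (SAP 4.7.3) |
| Creatinine, potassium | none | none |
| PCSA counts | not applicable | none |

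The baseline gaps arise because SAP 5.3.1 sends other baseline safety parameters to the safety summaries, and those summaries are not in Appendix 6.

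**3. When the data were due (SAP 5.7.1).**
- Weight and vital signs: screening, baseline, Week 12, Week 24.
- HbA1c and FPG: the same four visits. Appendix 6 keeps box plots of both by visit, and Listing 16.2.8 covers HbA1c, SMPG and FPG at Week 24.
- Clinical chemistry: screening and Week 24 only.
- Hematology and urinalysis: screening only.
- Patients who withdraw prematurely are to undergo the end-of-trial assessments, which include chemistry and vital signs.

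**4. Follow-up available by termination.** The first randomization was on 20 December 2022 (SAP version history) and termination on 27 June 2023 (SAP 1.1).
- 27 June 2023 − 20 December 2022 = 189 days = 27.0 weeks.
- Week 12 (Day 84) was reachable if randomized by 27 June 2023 − 84 days = 4 April 2023. That is a recruitment window of 189 − 84 = 105 days.
- Week 24 (Day 168) was reachable if randomized by 27 June 2023 − 168 days = 10 January 2023. That is a window of 189 − 168 = 21 days.

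Weight and vital signs therefore had a post-baseline visit that could be reached over 15 weeks of recruitment. Scheduled on-treatment chemistry could be reached from only the first three weeks of it, apart from early-discontinuation draws.

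**The case against.** The strongest reply is that the reduction is disclosed and reasoned. SAP 4.1 gives lack of data as the cause, and Appendix 2 points to an itemised list. A stated focus on safety does not promise every safety analysis. For chemistry this carries weight: the trial stopped for severe recruitment delay, and only a 21-day randomization window allowed a scheduled Week 24 draw by termination. The early-discontinuation visit may not fill the gap. It is written for patients who withdraw from the trial, and Protocol 11.3 sets no assessments for termination by the sponsor.

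A second reply is that important changes would still surface. Protocol 6.2.5 requires investigators to review laboratory reports and record clinically relevant changes. Its exceptions bring back symptomatic, treated, serious or special-interest findings, and those judged significant by the investigator. Such events would reach the retained adverse-event tables and Listing 16.2.7.1.

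Both replies limit the point without removing it. Lack of data does not explain keeping HbA1c and FPG plots from the same clinic visits while dropping weight and vital signs. Sparse chemistry argues for a listing rather than for no output. Event reporting does not show measured changes that fall below its criteria.

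A reader might infer that weight, eGFR and ALT appear nowhere in the report. That is not supported, because baseline weight, baseline eGFR and ALT-increase events are in retained tables. Nor can the laboratory values be called named endpoints: they are planned analyses outside the endpoint row.

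**Conclusion.** The point holds for post-baseline data. None of the 36 outputs reports post-baseline body weight, heart rate or blood pressure, which are named safety endpoints. None reports post-baseline creatinine, eGFR, ALT or potassium values, or any PCSA count, all of which SAP 4.7.4.1 planned. Appendix 2 does not name these analyses as dropped. The case is firmest for weight and vital signs, which have a Week 12 visit, and weaker for chemistry.

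It would go too far to infer that the report will be silent on renal or hepatic safety, since clinically relevant events remain reportable. What it will lack is any measured change in weight, vital signs or kidney function on either insulin.

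This rests on three assumptions: retained tables follow their SAP definitions, no output is planned outside Appendix 6, and visits ran to schedule. The documents do not give the number randomized or the number with post-baseline values, so the amount of information lost cannot be sized. The change should be made, but it bears on completeness of safety reporting and not on any inferential conclusion.

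**What to change.** 1. Add to Appendix 6 a Safety Set table of value and change from baseline at Week 12, at Week 24 and for the last on-treatment value, for body weight, SBP, DBP and heart rate. Show the number assessed and PCSA counts, as SAP 4.7.4.1 specifies.
2. Add a by-participant listing, or a table if numbers allow, of baseline and post-baseline creatinine, eGFR, ALT and potassium. Flag PCSAs where Table 12 defines a criterion. Table 12 has none for potassium, so use the normal range there, as SAP 4.7.4.1 allows. State which equation the eGFR flags use: Table 12 refers to MDRD, while SAP 4.7.4.1 has the central laboratory use CKD-EPI.
3. Name in Appendix 2 any laboratory or vital-sign analysis that stays dropped, with the reason.

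The cost is one or two descriptive outputs built from specifications already written, possibly with small numbers, plus a short addition to Appendix 2.
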